### **B. Study Type and Design:**

B. This is a randomized, double blind, crossover, placebo-controlled, study containing a screening visit, a double-blind treatment phase, and an end-of-study visit. The participating site is the University of Kansas Medical Center where eligible subjects in the age group of 18-65 years will be enrolled. A total of 26 subjects with 1-8 migraines per month will be enrolled in a randomized double blind fashion.

Power calculations were performed and we found that twenty six subjects are required to have a 90% chance of detecting, as significant at the 5% level, an increase in the primary outcome (benefit vs. failure) from 25% in the control group to 65% in the experimental group.

C.

D. The study will consist of two visits (Visit 1 Screening/ Randomization and Visit 2 End-of-Study). Subjects will treat two of their migraine attacks with either the study drug or placebo in a double blinded, randomized, crossover fashion within a period of 8 weeks. Subjects who do not have any migraines attacks in the given 8 weeks period will be dropped from the study. Eligible

subjects will be enrolled from their usual office visits. At the Screening/ Randomization visit, subjects will provide a detailed medical and headache history, concurrent medications, demographics, a physical examination will be performed, vital signs will be obtained, a urine pregnancy test will be obtained for female subjects with child bearing potential, and verification of inclusion/exclusion criteria will be completed. Since most of the above are done as a part of the routine office visit (except for urine pregnancy screen and verification of inclusion/ exclusion criteria), collection of these data points will not be repeated.

E.

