### **C. Sample size, statistical methods, and power calculation**

1. A total of 26 subjects will be enrolled. Eligible subjects in the age group of 18-65 years will be enrolled at the University of Kansas Medical Center. Subjects will be randomized on 1:1 ratio. They will treat their first migraine episode with the first drug (study drug or placebo, depending upon which group they are randomized to) and then will cross over to the second drug.
2. This will be a double-blinded study. The drug bottles (study drug and placebo) will be given to the subjects in unlabeled bottles.
3. A maximum of 26 subjects will be enrolled in the study. All data collected from the subjects will be entered on a secured spreadsheet/ database. Descriptive statistics will establish baseline characteristics and adverse event frequency. Data for the primary endpoint will be statistically analyzed via 2-tailed t-test. Data for the secondary outcome measures will be statistically analyzed for both within and between group changes via 2-tailed repeated measures ANOVA and or independent or dependent t-tests as appropriate. All ANOVAs will be followed by univariate post-hoc tests.
4. Study results:  
Primary outcome change in visual analogue pain scale (VAS) 120 minutes after dose showed a similar decreases for placebo and drug with a slightly wider 95% CI for placebo. Planned secondary analysis based on satisfaction (satisfactory and very satisfactory compared to neutral and unsatisfied) was negative by Chi-square  
Post-hoc analysis was 50% or greater decrease in VAS compared to < 50% decreased was negative by chi-square

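### The stated 90% power for 25% versus 65% is reached with 26 subjects only under a favourable assumption that the plan does not state; two-sided and uncorrelated, 26 completed pairs give about 75–82%

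*Combined protocol and SAP*

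**What the plan says.** The only sample-size justification is in section II.B: "twenty six subjects are required to have a 90% chance of detecting, as significant at the 5% level, an increase in the primary outcome". The outcome and effect follow directly: "benefit vs. failure) from 25% in the control group to 65% in the experimental group". Significance is given only as "as significant at the 5% level", with no sidedness, no named test and no correlation between a subject's two attacks.

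The rest of the plan supplies part of what is missing:

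- **Design.** Sections II.B and II.C describe a two-period crossover. Every subject treats one attack with each product, so 26 subjects give 26 observations per treatment.
- **Test.** Section II.C says "Data for the primary endpoint will be statistically analyzed via 2-tailed t-test", and sections II.B and V.A repeat this. Whether the primary t-test is paired or independent is not stated.
- **Ceiling.** Section II.C says "A maximum of 26 subjects will be enrolled in the study".
- **Losses.** Section II.B says "Subjects who do not have any migraines attacks in the given 8 weeks period will be dropped from the study". Sections II.D and II.L also withdraw subjects who have an adverse event. No expected loss rate or allowance is given.

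**The concern.** A power statement should be reproducible from its own inputs and from the analysis planned elsewhere in the document. Here the inputs are two proportions, a 5% level and 26 subjects, and the planned test is two-tailed. The common two-sided calculations on those inputs fall short of 90%.

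What is at stake is how a negative result is read. On the stated figure, a reader would allow a 10% chance of missing a 40-point difference. Section II.C already reports similar pain decreases on drug and placebo, so readers may well lean on the 90% when they judge that result.

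**Working it through.** **Inputs.** From section II.B: p1 = 0.25, p2 = 0.65, difference 0.40, 5% level, 26 subjects, each treated with both products. From section II.C: two-tailed testing. Not in the documents, so assumed and varied: the within-subject correlation phi and the number of completed pairs.

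**1. Trying to reproduce 90%: 26 independent observations per treatment, two-sided.**

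- Unpooled formula: n = (1.960 + 1.2816)² × (0.25×0.75 + 0.65×0.35) / 0.40² = 10.507 × 0.415 / 0.16 = 27.3, so 28 per treatment for 90%. At n = 26, SE = √(0.415/26) = 0.1263 and power = Φ(0.40/0.1263 − 1.960) = Φ(1.206) = 88.6%. Enumerating all outcomes for the same test gives 88.1%.
- Pooled formula: the null SE is √(2×0.45×0.55/26) = 0.1380, and power = Φ((0.40 − 1.960×0.1380)/0.1263) = 84.7%. It needs 31 per treatment for 90%.
- Full enumeration: Fisher 77.0%; chi-square 84.0%; independent t-test 84.0%.

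The closest of these is the unpooled calculation, and it still asks for 28 rather than 26.

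**2. The documented design: 26 pairs, two-sided, phi = 0.**

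Benefit on both treatments has probability 0.25×0.65 = 0.1625. The discordant cells are 0.65 − 0.1625 = 0.4875 and 0.25 − 0.1625 = 0.0875, together 0.575. The McNemar normal formula gives Φ((0.40√26 − 1.960√0.575)/√(0.575 − 0.16)) = Φ(0.859) = 80.5%. Enumeration gives 75.5% for exact McNemar and 82.4% for asymptotic McNemar or the paired t-test. By enumeration, 90% needs 32 pairs (asymptotic McNemar or paired t) or 36 pairs (exact).

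**3. What correlation would rescue 90%?**

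The joint probability of benefit rises by phi × √(0.1875×0.2275) = 0.2065 × phi. With these margins phi cannot exceed (0.25 − 0.1625)/0.2065 = 0.42. Two-sided power for 26 pairs, by enumeration:

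| phi (assumed) | discordant proportion | exact McNemar | asymptotic McNemar or paired t |
|---|---|---|---|
| 0 | 0.575 | 75.5% | 82.4% |
| 0.1 | 0.534 | 79.8% | 86.1% |
| 0.2 | 0.492 | 84.9% | 90.2% |
| 0.3 | 0.451 | 90.7% | 94.7% |

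**4. What would a one-sided 5% test do?**

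With phi = 0, 26 pairs give 90.5% (asymptotic McNemar) or 85.3% (exact McNemar). With 26 per treatment unpaired, chi-square gives 93.0%, and the pooled formula gives 91.5% and needs 25.

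**5. What do losses do?**

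The documents give no loss rate. As an illustration only, assume 22 completed pairs with phi = 0: two-sided power is 65.5% (exact McNemar), 74.2% (asymptotic McNemar) or 77.4% (paired t).

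**The case against.** The strongest defence is that the sentence is incomplete rather than wrong. Two-sided testing and zero correlation are supplied by whoever checks it, because the power sentence states neither. Two attacks in the same person may well respond alike, and a phi of 0.2 to 0.3, within the possible maximum of 0.42, recovers 90%. A one-sided calculation can also reach it, and the effect is worded as an increase. The 75% end of the range comes from exact McNemar, a conservative test that the plan does not mention. The plan also calls the trial a pilot.

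Much of this stands. A reader might infer that the calculation is simply an arithmetic error or that 26 subjects cannot give 90%. The documents do not support that, because 90% is attainable under a modest positive correlation.

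A reader might also take the control-group and experimental-group wording to mean 13 subjects against 13, where two-sided power is only 46% (Fisher) to 63% (chi-square). That is not this trial: each subject crosses over and contributes to both treatments.

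The defence does not restore the figure as stated. Two-sidedness comes from the plan's own analysis sections, so a one-sided power calculation would itself be an inconsistency. The t-test family that the plan does name gives 82% paired and 84% unpaired without correlation. And if 90% rests on a correlation, that correlation is a design input that should be written down.

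**Conclusion.** The concern holds in this form: the plan's only sample-size justification states a power that its inputs, with the planned two-sided testing, do not deliver unless a favourable assumption is added that is nowhere stated. With no correlation, the chance of missing the 25% versus 65% difference is about 18–25% on the paired tests, and about 12% at best (unpooled test, observations treated as independent), instead of 10%.

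The 26 subjects are both the number said to be required and the most that may be enrolled. Any subject who does not treat two attacks therefore takes power below these figures. A subject with a single attack yields no pair either, even though the drop rule covers only those with none.

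Two limits apply. Phi and the number of completed pairs are assumptions, since the documents give neither. And the check concerns the binary comparison as section II.B states it. Section V.B defines the primary endpoint as headache severity at 120 minutes; the power for that comparison cannot be worked out from the documents, and nothing here shows that the reported result was due to low power.

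**What to change.** Keep 26 subjects and restate the power in section II.B along these lines: *26 completed pairs give about 75–82% power (two-sided 5%, no within-subject correlation) to detect 25% versus 65%, rising to about 85–90% at phi = 0.2 and 91–95% at phi = 0.3.*

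Name the paired test, and then give the figures for that test alone. For exact McNemar they are 75%, 85% and 91%; for asymptotic McNemar or paired t they are 82%, 90% and 95%. State that the figures are for completed pairs and that 26 includes no allowance for losses. If 90% is to be kept, state the test and the correlation on which it depends, with a planning-stage source. The correlation should not be taken from the trial's own results.

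The cost is one sentence and a less favourable stated power. It requires no extra patients and no change to the design.

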**Table 1: Schedule of events**

Procedure	Baseline Visit	Interim Visit	End of Study Visit
Consent	X		
Demographics	X		
Medical History	X		
Concomitant Medications	X	X	X
Physical Exam	X		X
Vital signs	X		X
Urine pregnancy screen	X		X
Drug Dispensing	X	X	
Drug Accountability		X	X
Adverse events		X	X
Pain Questionnaire	X	X	X
Satisfaction Questionnaire	X	X	X
Data Entry	X	X	X

At any point, during the treatment of their migraine attacks with the study medications, rescue medications (like NSAIDs, triptans or their usual migraine abortive medications) can be taken 120 minutes after the study drug dose, if necessary. After treating their second migraine attack, the subjects will return for an end-of-study visit. This should occur within 7 days after treating their last qualifying migraine, or after 8 weeks of enrolling in the study (whichever comes first). The subject's diary information will be reviewed and all end-of-study visit procedures will be performed

Subjects will use a diary to collect all attack and safety data needed for data analysis. They will use the comparative pain scale to grade their migraine pain level before and at 2 hour after administration of study ophthalmic drops. They will be provided forms during each visit to record their pain score and treatment satisfaction. A safety monitor will be appointed and all adverse reactions will be reported, although we do not anticipate any adverse events given the short duration of the study and established safety of the drug. All data collected from the patients will be entered on a secured spreadsheet/ database. No patient identifiers will be used. Descriptive statistics will establish baseline characteristics and adverse event frequency. Data for the primary endpoint will be statistically analyzed via 2-tailed t-test. Data for the secondary outcome measures will be statistically analyzed for both within and between group changes via 2-tailed repeated measures ANOVA and or independent or dependent t-tests as appropriate. All ANOVAs will be followed by univariate post-hoc tests.

### **C. Sample size, statistical methods, and power calculation**

1. A total of 26 subjects will be enrolled. Eligible subjects in the age group of 18-65 years will be enrolled at the University of Kansas Medical Center. Subjects will be randomized on 1:1 ratio. They will treat their first migraine episode with the first drug (study drug or placebo, depending upon which group they are randomized to) and then will cross over to the second drug.
2. This will be a double-blinded study. The drug bottles (study drug and placebo) will be given to the subjects in unlabeled bottles.
3. A maximum of 26 subjects will be enrolled in the study. All data collected from the subjects will be entered on a secured spreadsheet/ database. Descriptive statistics will establish baseline characteristics and adverse event frequency. Data for the primary endpoint will be statistically analyzed via 2-tailed t-test. Data for the secondary outcome measures will be statistically analyzed for both within and between group changes via 2-tailed repeated measures ANOVA and or independent or dependent t-tests as appropriate. All ANOVAs will be followed by univariate post-hoc tests.
4. Study results:  
Primary outcome change in visual analogue pain scale (VAS) 120 minutes after dose showed a similar decreases for placebo and drug with a slightly wider 95% CI for placebo. Planned secondary analysis based on satisfaction (satisfactory and very satisfactory compared to neutral and unsatisfied) was negative by Chi-square  
Post-hoc analysis was 50% or greater decrease in VAS compared to < 50% decreased was negative by chi-square

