F. Subjects who meet all inclusion and exclusion criterion will be identified and recruited through routine office visits. Subjects will be randomized in a double-blinded fashion to either the study medication arm or placebo arm. They will be sent home with one bottle of the drug, which will be either the study medication (0.5% timolol ophthalmic solution) or the placebo (0.9% normal saline solution). They will be provided instructions on proper administration of the eye drops. They will treat their first migraine attack with 1 drop of ophthalmic solution in each eye (either study medication or placebo, depending upon which study arm they are in). If they miss the eye in the first attempt, they may re-administer another drop. They will be asked to then blink rapidly for 3-5 seconds to promote absorption. After 15 minutes, if the migraine headache is still present, they can re-administer one drop in each eye. They will record their migraine pain level using the comparative pain scale (Appendix B) before administering the eye drops and 2 hours after treatment. They will also report their treatment satisfaction using the forms provided (Appendix C). After the treatment of their first migraine attack, the subjects will notify the study staff and will either come in to return the first bottle and forms or they will send in their medications and forms. Once the first bottle is received, we will either mail in using a service like FedEx or they will return to pick up their second bottle. At the interim visit, if the subjects decide to return their first bottle via mail, they will be contacted by the study staff via phone call, in order to report any changes in their concomitant medications or any adverse events. The subjects will treat their second migraine attack with the second drug and again report their migraine pain level using the comparative pain scale and also report treatment satisfaction. See table below.

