## **V. Data Analysis and Reporting**

**A. Statistical and Data Analysis:** All data collected from the patients will be entered on a secured spreadsheet/ database. No patient identifiers will be used. Descriptive statistics will establish baseline characteristics and adverse event frequency. Data for the primary endpoint will be statistically analyzed via 2-tailed t-test. Data for the secondary outcome measures will be statistically analyzed for both within and between group changes via 2-tailed repeated measures ANOVA and or independent or dependent t-tests as appropriate. All ANOVAs will be followed by univariate post-hoc tests.

**B. Outcome:** The primary end point of the study is to compare differences in headache severity at 120 minutes between study medication and placebo. A statistically significant pain relief in the study medication arm when compared to the placebo arm will determine success of the study. The secondary end point will be to assess the safety and subject satisfaction with treatment.

**C. Study results to participants:** Once the study results are available, they will be conveyed to the subjects either in person during their regular office visit or via telephone calls

**D. Publication Plan:** We plan to publish the study upon completion and results available.

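### The crossover's success-deciding test is given only as a two-tailed t-test; the plan should name a within-subject, period-adjusted comparison, and the report should say which t-test was run

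*Combined protocol and SAP*

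**What the plan says.** **Design.** II.B states: "Subjects will treat two of their migraine attacks with either the study drug or placebo in a double blinded, randomized, crossover fashion". It continues: "The subjects will treat their second migraine attack with the second drug and again report their migraine pain level using the comparative pain scale". II.C.1 says that subjects take the first drug "and then will cross over to the second drug". Each subject therefore supplies one outcome per treatment.

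**Primary test.** II.B, II.C.3 and V.A use the same sentence: "Data for the primary endpoint will be statistically analyzed via 2-tailed t-test". None of them mentions pairing, a within-subject difference, period or sequence.

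**Success rule.** V.B: "A statistically significant pain relief in the study medication arm when compared to the placebo arm will determine success of the study".

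**Secondary outcomes.** These are analysed for "within and between group changes via 2-tailed repeated measures ANOVA and or independent or dependent t-tests as appropriate" (V.A; same sentence in II.B and II.C.3).

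**Results.** II.C.4 says that the primary outcome, there called change in VAS at 120 minutes, "showed a similar decreases for placebo and drug with a slightly wider 95% CI for placebo". It gives no between-treatment difference and no interval for one. It also reports satisfaction (planned secondary) and a response of 50% or more (post hoc) as negative on a chi-square test. The analysis plan names no such test.

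**The concern.** A crossover gains its efficiency from comparing each subject with himself or herself. The plan does not say that the deciding comparison does this. Dependent tests are mentioned only for secondary outcomes, and there as one option beside independent ones. The power statement, "from 25% in the control group to 65% in the experimental group", and the success rule are worded as for parallel groups. Two analysts following this plan could run t-tests with different error rates, power and interval widths on the same data, and V.B makes the significance of that test the definition of success.

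Because the reported result is null, the main stake is power and the width of the interval. A null result from an independent-samples test on positively correlated pairs is less informative than the same data allow.

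**Working it through.** **1. Inputs.** From the documents: two-period crossover, 26 subjects, 1:1 allocation, 5% level (II.B, II.C.1), two-tailed t-test (II.C.3). Not in the documents, so assumed: within-subject correlation r (range -0.2 to 0.5), equal SD σ under both treatments, a 0.6σ treatment effect, and 26 complete pairs.

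**2. Does the plan's sample size settle the question?** The plan gives 26 subjects for 90% power at 25% against 65%.
- Independent proportions, two-sided, unpooled: n = (1.960 + 1.282)² × (0.25×0.75 + 0.65×0.35) / 0.40² = 10.51 × 0.415 / 0.16 = 27.3, so 28 per treatment. Power with 26 outcomes per treatment is 88.6%. The one-sided pooled formula gives 25 per treatment.
- McNemar, two-sided, normal approximation: n runs from 22 (no subject responds to placebo alone) through 34 (correlation 0) to 55 (25% respond to placebo alone). It equals 26 only if about 3% respond to placebo alone, a figure that the plan does not give.

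So 26 is near an unpaired formula read per treatment and is also compatible with a paired one. It does not show which analysis was intended.

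**3. Effect of ignoring pairing on the primary test.** The standard error of the mean difference is
- as computed by an independent-samples test: σ√(2/26), whatever r is;
- true, and as estimated by a paired test: σ√(2(1−r)/26).

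Paired power comes from the noncentral t with 25 df (critical value 2.060) and noncentrality 0.6√26 / √(2(1−r)). At r = 0.3 this is 3.059/1.183 = 2.586, giving 70.0%. At r = 0.5 it is 3.059/1.000 = 3.059, giving 83.6%. Independent-samples figures are from simulation of correlated normal pairs. The between-sequence test is the t-test of within-subject period differences with 13 subjects per sequence (24 df), which adjusts for period.

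| r | -0.2 | 0 | 0.3 | 0.5 |
|---|---|---|---|---|
| Type I error, independent-samples | 7.3% | 5.0% | 2.0% | 0.7% |
| Type I error, paired or between-sequence | 5.0% | 5.0% | 5.0% | 5.0% |
| Power, independent-samples | 55.9% | 56.5% | 57.6% | 59.0% |
| Power, paired | 47.6% | 54.8% | 70.0% | 83.6% |
| Power, between-sequence | 47.4% | 54.6% | 69.9% | 83.5% |
| Mean 95% CI half-width, independent-samples (σ) | 0.55 | 0.55 | 0.55 | 0.55 |
| Mean 95% CI half-width, paired (σ) | 0.62 | 0.57 | 0.47 | 0.40 |

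With an assumed 0.5σ period effect at r = 0.3, the paired test falls to 63.5% and the between-sequence test stays at 69.9%. Adjusting for period when there is no period effect costs 0.1 to 0.2 points. With 20 complete pairs at r = 0.3, independent-samples power is 44.9% and paired power 57.6%.

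**4. The binary results (illustration only).** No counts are given. Assume 8/26 responders on one treatment and 14/26 on the other. The pooled proportion is 22/52 = 0.423, so z = (6/26) / √(0.423 × 0.577 × 2/26) = 0.2308/0.1370 = 1.68, and the Pearson chi-square p is 0.092. Nine paired tables have these totals. With discordant counts 1 and 7, McNemar mid-p is 0.039 (exact 0.070). With 0 and 6, mid-p is 0.016 (exact 0.031). The other seven are non-significant, in agreement with the chi-square. The choice of test can matter, but usually does not in this example.

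**The case against.** The strongest defence is that this is an omission of detail and not a wrong test. A two-tailed t-test includes the paired one. The study is called a crossover, and the very next sentence names dependent t-tests and repeated measures ANOVA, so the authors knew of them. Arm is weak evidence of a parallel-group analysis, because II.B also uses study arm for the treatment assigned first within the crossover. The trial is a pilot, its results are already reported, and they are null. With complete pairs, pairing leaves the mean difference as it is and changes only its standard error. Rewriting the plan now cannot restore prespecification.

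Much of this stands. A reader might infer that an unpaired t-test was run; the documents do not show that. A reader might infer inflated false-positive risk; that needs a negative within-subject correlation, which nothing in the documents suggests, and the reported result is not positive. Nor is the phrase about independent or dependent tests an error in itself, since the period-adjusted crossover test is an independent t-test between sequences.

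What does not stand is the claim that the context fills the gap. The sentence on dependent tests covers secondary outcomes only and leaves the choice open. Both reported binary results came from a chi-square test that the plan does not name, so it cannot be assumed that a paired method was used wherever the plan was silent.

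**Conclusion.** The concern holds as an underspecified primary analysis that should be fixed. It is not a demonstrated error, and the null, already reported result does not justify calling it critical. The test that decides success admits an independent-samples analysis of paired data, and II.C.4 does not say which was used.

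If the within-subject correlation is 0.3 to 0.5, the independent-samples test gives up about 12 to 25 points of power (70.0 − 57.6 = 12.4; 83.6 − 59.0 = 24.6), and its interval is about 1.2 to 1.4 times as wide (0.55/0.47; 0.55/0.40). At zero correlation there is nothing to gain. These figures rest on the assumed 0.6 SD effect, the assumed correlations and 26 complete pairs; none of these is in the documents.

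It might be tempting to conclude that the null finding would turn positive under a paired analysis. The documents give neither a correlation nor paired data, so they do not support that. For the two binary results, the unpaired chi-square is the natural reading but McNemar's test is not excluded. Neither result decides success, and for them this is only a request for clarification.

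**What to change.** **Plan wording (II.B, II.C.3, V.A).** Replace the primary-test sentence with, for example:

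> The primary outcome of V.B, headache severity at 120 minutes (reported in II.C.4 as change in VAS), is compared between timolol and placebo within subject by a mixed model with treatment, period and random subject, two-sided at 5%. Subjects with one treated attack are kept, including those withdrawn after an adverse event. A paired t-test on complete pairs is a sensitivity analysis. [Added after results were known.]

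Naming the outcome matters because the specific aims give headache freedom at 2 hours and the power statement a binary benefit. Keeping one-attack subjects matters because II.D.3 and II.L withdraw subjects with adverse events. A complete-pair test would lose anyone withdrawn after the first attack, and that loss may depend on treatment.

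**Results (II.C.4).** State which t-test was used. Add the timolol-minus-placebo difference, its 95% CI and the number of complete pairs. State whether the chi-square was McNemar's. If it was not, re-run both binary results with McNemar's test (mid-p), show the four paired counts, and present them beside the originals. Label every addition as made after results were known.

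**Cost.** A few sentences and a small re-analysis of existing data. If the correlation is near zero, the within-subject analysis has slightly less power (paired 54.8% against about 56.5%). At -0.2 the loss is larger (47.6% against 55.9%), but the independent-samples test then has 7.3% type I error. If a paired test was in fact used, one sentence and one interval settle the primary question.

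### Satisfaction is reported from a two-class chi-square that the plan text does not specify; the split loses some power against the score-based paired methods the plan does state

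*Combined protocol and SAP*

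**What the plan says.** Section V.B makes satisfaction a secondary endpoint: "The secondary end point will be to assess the safety and subject satisfaction with treatment". Section II.B has each patient record it on the Appendix C form for each of the two treated attacks. That form is not in the text available for this review.

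The method for secondary outcomes is given three times in the same terms: in II.B after the schedule of events, in II.C item 3, and in V.A. Secondary outcomes are to be "statistically analyzed for both within and between group changes via 2-tailed repeated measures ANOVA and or independent or dependent t-tests as appropriate". These methods work on the score itself.

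The design is a crossover. Section II.C states that "A total of 26 subjects will be enrolled", and that patients treat the first attack with one drug "and then will cross over to the second drug".

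Item 4 of II.C gives results. For satisfaction it says: "Planned secondary analysis based on satisfaction (satisfactory and very satisfactory compared to neutral and unsatisfied) was negative by Chi-square". The next sentence reports a split of the pain score and labels that one post hoc.

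**The concern.** Two adjacent items of one section do not agree. Item 3 names ANOVA and t-tests. Item 4 names a chi-square on two classes and calls the analysis planned. A reader of item 4 alone may take the cut-point as fixed in advance, and the plan text does not show that it was.

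The cut also discards information. Item 4 shows four ordered labels. After the split, a patient who is unsatisfied on one treatment and neutral on the other counts as unchanged, and so does a move between the two favourable labels. With at most 26 patients, that can turn a moderate shift into a non-significant result. At stake is how much weight the reported negative satisfaction result can bear in a pilot that is meant to inform larger trials.

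**Working it through.** **1. The plan's own figure.** The only power statement (II.B) is for the primary outcome: 25% against 65%, 5% level, 90% power, 26 subjects. The two-sided unpooled formula gives n = (1.960 + 1.282)² × (0.25×0.75 + 0.65×0.35) / 0.40² = 10.51 × 0.415 / 0.16 = 27.3 per condition. With 26 per condition, power is 88.6%. So 26 is roughly reproduced if every patient contributes to both conditions. It says nothing about power for satisfaction.

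**2. Stated method against reported method.**

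| | II.B, II.C item 3, V.A | II.C item 4 |
|---|---|---|
| Data used | score | two classes |
| Test | repeated-measures ANOVA and/or t-tests | chi-square |
| Cut-point | none | between neutral and satisfactory |
| Pairing | dependent t-test allowed | not stated |

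**3. Inputs for the power check.** From the documents: 26 patients, each rating both treatments; 5% level; two-tailed tests; four visible labels. Assumed, because the documents are silent: placebo distribution 40/30/20/10% from unsatisfied to very satisfactory; a latent normal shift of 0.6 SD; within-patient correlation 0, 0.3 or 0.5; all 26 pairs complete.

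**4. Hand check at correlation 0.** The cut lies at Φ⁻¹(0.70) = 0.524. Satisfied on placebo: 30%. Satisfied on timolol: 1 − Φ(0.524 − 0.6) = 53%.
- *Chi-square.* The pooled proportion is 0.415. The standard error is √(2×0.415×0.585/26) = 0.137 under no effect and √((0.30×0.70 + 0.53×0.47)/26) = 0.133 under the shift. Power = Φ((0.230 − 1.96×0.137)/0.133) ≈ Φ(−0.28) ≈ 39%.
- *Dependent t-test on scores 1 to 4.* Placebo mean 2.00, variance 1.00. Timolol category probabilities 0.197, 0.273, 0.282 and 0.248 give mean 2.58 and variance 1.13. The SD of the difference is √(1.00 + 1.13) = 1.46. Noncentrality = 0.58 × √26 / 1.46 = 2.03 against a critical value of 2.06, so power ≈ 49%.

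**5. Simulation of the same set-up** (8,000 replicates per row, Monte Carlo error about 0.6 points per entry), 0.6 SD shift:

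| Correlation | Paired t, full score | Wilcoxon signed-rank, full score | McNemar mid-p, cut | Mann-Whitney, full score | Chi-square unpaired, cut |
|---|---|---|---|---|---|
| 0 | 49% | 48% | 36% | 50% | 39% |
| 0.3 | 61% | 60% | 42% | 50% | 38% |
| 0.5 | 74% | 72% | 49% | 51% | 38% |

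Mid-p McNemar is used because exact McNemar rejects only about 2% of the time under no effect. Its 33% power at correlation 0.3 would therefore overstate the cost of the cut.

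**6. Separating the sources of loss at correlation 0.3.**
- Cut alone, unpaired tests: 50 − 38 = 12 points.
- Cut alone, paired tests: 60 − 42 = 18 points.
- Cut plus lost pairing: 60 − 38 = 22 points. The same comparison is 48 − 39 = 9 points at correlation 0 (repeat runs gave 7 to 9) and about 35 at 0.5.

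**7. A different model.** With proportional odds, odds ratio 3, and four or five levels under several placebo distributions, the cut alone moved power from 55–61% to 42–48% unpaired. Paired, it moved from 52–56% to 37–46% at correlation 0 and from 76–83% to 50–62% at correlation 0.5. At odds ratio 5.57 (the odds ratio of 65% against 25%), chi-square reached 73–89% and signed-rank 88–99%. The direction was the same in every scenario with an effect.

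**The case against.** The strongest reply has four parts.

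*The size of the loss is not in the documents.* This stands. A reader might infer that the split threw away much of the endpoint's power as an established fact. The documents give no distribution, correlation, effect size or number analysed. Patients without attacks are dropped, so 26 pairs is a ceiling. Comparing a paired full-score test with an unpaired split also charges lost pairing to the cut.

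*The word planned may be innocent.* It contrasts with the post hoc label in the next sentence and may mean only that satisfaction was a planned secondary endpoint, which V.B confirms. This stands as a possible reading. The documents do not show that the cut was chosen after seeing the data. They also do not show that it was chosen before.

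*Grouping neutral with unsatisfied is natural.* This is fair. Item 4 compares two groups and does not call neutral a failure, so that stronger reading is not supported.

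*Little depends on it.* The study is a self-described pilot, V.B ties success to pain relief, and item 4 reports similar pain decreases on both treatments. This limits the importance of the point but does not remove the conflict between items 3 and 4.

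**Conclusion.** The mismatch is established from the text: the reported cut and test for satisfaction appear in none of the sections that state the analysis methods. The loss of power from splitting is certain in direction and uncertain in size. Under the assumptions above it is about 12 points unpaired or 18 points paired at correlation 0.3, and it shrinks when effects are large enough for power to be high either way. Whether lost pairing adds to it depends on how the chi-square was run, which the documents do not say.

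A reader might go further and infer that a real satisfaction benefit was missed. Nothing supports that. Low power makes the negative result weak evidence and does not point to an effect. The point concerns a secondary endpoint, and no stated decision rests on it.

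**What to change.** Reconcile items 3 and 4 of II.C, and state where the cut and the chi-square were specified, if anywhere. Analyse the full satisfaction score within patient by the method already in the plan: a dependent t-test on the timolol-minus-placebo difference, or the repeated-measures ANOVA. In the check above the t-test did as well as Wilcoxon (61% against 60%), so no new primary method is needed for this endpoint. A Wilcoxon signed-rank test can be a sensitivity analysis for the ordinal scale, labelled as added after the results were known.

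Keep the two-class split as a description, shown as a paired table and labelled as not specified in the plan text. Describe its negative result as limited evidence, with an estimate and interval from the full-score analysis beside it.

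The cost is some wording and one re-run on data already collected. The small downside is that the re-analysis follows a reported negative result, and the report must say so.
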